5.5.10.3. Secondary and Exploratory Efficacy Analyses

Key secondary efficacy measures will be tested in the order as specified in Section 5.5.10.4

Table CGAW.5.5 summarizes all the planned secondary and exploratory efficacy analyses for SP III and SP III/IV, not including analyses for health outcome measures. Additional statistical analysis details are also provided below.

Continuous Efficacy Measures

For the continuous secondary efficacy measures, the change from baseline will be estimated from MMRM as described for analysis for primary outcome or ANCOVA as described in Section 5.5.1.1.

For continuous secondary efficacy measures where the objective is to assess overall mean change during 3-month double-blind treatment phase, the endpoint for galcanezumab compared with placebo will be estimated as the treatment main effect from the MMRM analysis assessing the average treatment effect across Months 1, 2, and 3.

Binary Efficacy Measures

For the repeated binary efficacy measures such as responder indicators based on the number of migraine headache days, the visit-wise binary outcomes indicating whether patients meet X% response criteria will be analyzed using a categorical, pseudo-likelihood-based repeated measures analysis. This analysis will be implemented using the GLIMMIX procedure in SAS to compare treatments with covariates adjustment described in Section 5.5.1.1.

An unstructured covariance structure will be used to model the within-patient errors (denoted by TYPE=CHOL in the RANDOM statement). The Newton-Raphson method with ridging will be used for nonlinear optimization (denoted by including NLOPTIONS TECH=NRRIDG). The Kenward-Roger approximation will be used to estimate denominator degrees of freedom. If the

model does not converge, the Fisher's scoring algorithm will be utilized by the SCORING option in SAS.

If the model still fails to converge, the model will be fit using covariance matrices in the following order specified by a decreasing number of covariance parameters until convergence is met:

- Heterogeneous Toeplitz,
- Heterogeneous autoregressive,
- Toeplitz, and
- Autoregressive.

If necessary, both fitting algorithms will be used in the pre-specified order before proceeding to the next covariance structure in the sequence.

For models where the unstructured covariance matrix is not utilized, the sandwich estimator (Diggle et al. 1994) will be used to estimate the standard errors of the fixed effects parameters. The sandwich estimator is utilized by the EMPIRICAL option in SAS. When the sandwich estimator is utilized, the Kenward-Roger approximation for denominator degrees of freedom cannot be used. Instead, the denominator degrees of freedom will be partitioned into between-subject and within-subject portions by the DDFM=BETWITHIN option in SAS.

For the binary secondary efficacy measures where the objective is to assess proportion of patients with X% response during the 3-month double-blind treatment phase, the endpoint for galcanezumab compared with placebo will be estimated as the treatment main effect from the categorical MMRM analysis assessing the average response rate across Month 1, Month 2, and Month 3.

The number of weekly migraine headache days in Month 1

If statistically significant improvement is observed at Month 1 and maintained for all the subsequent months during the double-blind treatment phase for the number of monthly migraine headache days, the number of weekly migraine headache days in Month 1 will be analyzed to identify the earliest week where the statistically significant improvement is observed and maintained for all the subsequent weeks in Month 1 for patients who have a monthly diary compliance rate greater than 50% for Month 1.

The number of weekly migraine headache days in Month 1 can be considered as ordinal data with possible values of 0, 1, 2, 3, 4, etc. and will be analyzed using an ordinal repeated measures model using the GLIMMIX procedure in SAS. In this model, a proportional odds model with cumulative logit link will be used, and a random intercept will be applied to the observations for each patient to account for repeated measures. The model will include the fixed, categorical effects of treatment, pooled country, week, and treatment-by-week interaction, as well as the continuous, fixed covariate of weekly baseline number of migraine headache days and weekly baseline number of migraine headache days-by-week interaction. Log (number of compliant calendar days within each week/7) will be included as the offset in the model. For weekly diary

compliance rate ≤50%, the number of weekly migraine headache days during that week will be considered missing.

The weekly baseline number of migraine headache days will be derived as (the monthly number of migraine headache days)/30*7.

Table CGAW.5.5. Secondary and Exploratory Efficacy Variables and Analysis Methods

Efficacy Variables	SP III	SP III/IV	
Number of migraine headache days (episodic)			
Number of migraine headache hours			
Number of migraine attacks (episodic only)			
Number of days with abortive medication use			
Number of days with triptan use			
Number of days with NSAIDs/aspirin use			
Number of days with acetaminophen/paracetamol use			
Number of days with ergot use			
Number of days with anti-nausea medication use			
Number of days with opioids and barbiturates use		MMRM	
Number of headache days	MMRM		
Number of headache hours			
Number of ICHD migraine headache days			
Number of migraine headache days with nausea and/or vomiting			
Number of migraine headache days with photophobia and phonophobia			
Number of migraine headache days with aura			
Number of migraine headache days prodrome symptoms other than aura			
Number of headache-free and symptom-free days			
Number of weekly migraine headache days in Month 1	GLIMMIX for ordinal outcome	NA	
X% response rate (X=30, 50, 75, or 100)*a	GLIMMIX	GLIMMIX	
Proportion of patients maintained 50% response in SP IV among all galcanezumab-treated 50% responders at Month 3	NA	Logistic regression	
Global Patient Impression – Severity	ANCOVA	MMRM	

[figure not shown]
Abbreviations: ANCOVA = analysis of covariance; GLIMMIX = Generalized linear mixed model (for categorical variables); MMRM = Mixed models repeated measures; N/A= Not applicable.

^{*}a 30% response rate is for chronic migraine subpopulation only.

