6.1. Inclusion Criteria

Patients are eligible to be included in the study only if they meet all of the following criteria at screening:

Patient and Disease Characteristics

- [1] Patients are 18 to 75 years of age (inclusive) at the time of screening.
- [2] Have a diagnosis of migraine as defined by IHS ICHD-3 guidelines (1.1, 1.2, or 1.3) (ICHD-3 2018), with a history of migraine headaches of at least 1 year prior to Visit 1, and migraine onset prior to age 50.
- [3] Prior to Visit 1, have a history of at least 4 migraine headache days and at least 1 headache-free day per month on average within the past 3 months.
- [4] Prior to Visit 1, have documentation (medical or pharmacy record or by physician's confirmation) of previous failure to 2 to 4 migraine preventive medication categories in the past 10 years from the following list due to inadequate efficacy (that is, maximum tolerated dose for at least 2 months) and/or safety/tolerability reasons.
 - a) propranolol or metoprolol
 - b) topiramate
 - c) valproate or divalproex
 - d) amitriptyline
 - e) flunarizine
 - f) candesartan
 - g) botulinum toxin A or B (if documented that botulinum toxin was taken for chronic migraine)
 - h) medication locally approved for prevention of migraine

Note: Patients only qualifying under the above criteria with f) and h) should not exceed 20% of the total study population.

- [5] From Visit 2 to Visit 3 (prospective baseline period), have a frequency of 4 or more migraine headache days and at least 1 headache-free day per 30-day period (see definitions in Table CGAW.3). To avoid biased reporting, patients will not be told the number of migraine or headache days on which study qualification is based.
- [6] From Visit 2 to Visit 3 (prospective baseline period), must achieve sufficient compliance with ePRO daily headache entries as demonstrated by completion of at least 80% of daily diary entries.

Informed Consent and Patient Agreements

- [7] Are able and willing to give signed informed consent.
- [8] Are reliable and willing to follow study procedures.
- [9] Women of child-bearing potential must test negative for pregnancy at the time of enrollment based on a serum pregnancy test.

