To compare galcanezumab with placebo with respect to 75% response rate	The percentage of patients with ≥75% reduction from baseline in monthly migraine headache days during the 3-month double-blind treatment phase	
To compare galcanezumab with placebo with respect to 100% response rate	The percentage of patients with 100% reduction from baseline in monthly migraine headache days during the 3-month double-blind treatment phase	

(Table CGAW.4.1. continued)

Objectives	Endpoints
Secondary Objectives Note: All other secondary objectives will be tested	
in both the total population (episodic and chronic migraine) and the episodic migraine subpopulation unless otherwise specified.	
To compare galcanezumab with placebo with respect to onset of effect	The initial month at which statistical separation in mean change from baseline in the number of monthly migraine headache days is demonstrated and maintained at all subsequent months through Month 3 in the double-blind treatment phase
	If the initial month of onset is Month 1, then the initial week at which statistical separation in mean change from baseline in the number of weekly migraine headache days is demonstrated and maintained at all subsequent weeks during Month 1
To compare galcanezumab with placebo with respect to change in use of acute headache treatment	The overall mean change from baseline in the number of monthly days with acute headache medication use during the 3-month double-blind treatment phase
To compare galcanezumab with placebo with respect to change in monthly headache days	The overall mean change from baseline in the number of monthly headache days during the 3-month double-blind treatment phase
To compare galcanezumab with placebo with respect to change in International Classification of Headache Disorders (ICHD) migraine headache days	The overall mean change from baseline in the number of monthly International Classification of Headache Disorders (ICHD) migraine headache days during the 3-month double-blind treatment phase
To compare galcanezumab with placebo with respect to change in monthly migraine headache hours	The overall mean change from baseline in the number of monthly migraine headache hours during the 3-month double-blind treatment phase
To compare galcanezumab with placebo with respect to change in monthly headache hours	The overall mean change from baseline in the number of monthly headache hours during the 3-month double-blind treatment phase

(Table CGAW.4.1. continued)

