The daily data will reflect whether the patients meet the migraine / probable migraine criteria; those data will be aggregated, and the number of migraine headache days will be provided for each of the 30-day periods. In calculating the number of migraine headache days for each period, if the period is not equal to 30 days, the number of migraine headache days will be adjusted by multiplying the number of migraine headache days by (30/x) where 'x' is the total number of non-missing diary days in the period.

This approach to missing ePRO diary data assumes that the rate of migraine headache per day is the same for days with missing and non-missing ePRO diary days. The same approach will also be applied to secondary and exploratory efficacy measures that are derived from ePRO data.

Additionally, if the compliance rate for a monthly interval is \leq 50%, then all endpoints to be derived from the ePRO diary data for that 1-month period will be considered missing. The compliance rate will be calculated as described in Section 5.5.7.

Other Secondary and Exploratory Efficacy Measures

The same approach for adjusting the number of days within each period to a 30-day period and the same approach to imputing monthly data based on compliance as for the primary measure will be applied to all efficacy measures that are derived from ePRO diary data and need normalization to a 30-day period, including:

- Number of ICHD migraine headache days is calculated as the number of calendar days in a 30-day period on which a migraine occurs. Probable migraine is excluded.
- **Number of headache days** is calculated as the number of calendar days in a 30-day period on which a headache occurs.
- **Number of migraine headache hours** is calculated as the total number of headache hours in a 30-day period on days when a migraine or probable migraine occurs.
- **Number of headache hours** is calculated as the total number of headache hours in a 30-day period on which a headache occurred.
- Number of days with acute headache medication use is calculated as the number of calendar days in a 30-day period on which abortive medication is used.

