5.5.7. Electronic Patient-Reported Outcomes Diary Compliance

Electronic patient-reported outcomes diary compliance at each 1-month period (including baseline, Month 1, Month 2, ... to Month 6) as well as for SP III overall (Month 1 through Month 3) will be calculated. Diary compliance at each 1-month period is calculated as:

 $\frac{\text{Actual number of diary days in the period}}{\text{Expected number of diary days in the period}}*100$

Expected number of ePRO diary days is calculated as date of injection at the end of the interval minus date of injection at the beginning of the interval +1.

For a patient who discontinues early in the double-blind (SP III) or open-label treatment phase (SP IV), compliance rate for the last month of that patient will be calculated with a denominator of 30 days (or the actual number of days in the interval if it is greater than 30).

Treatment comparisons for ePRO diary compliance for SP III will be performed using an ANOVA with treatment, baseline migraine frequency category, and pooled country in the model. ePRO diary compliance for SP IV will be summarized.

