To assess the robustness of the MMRM results to deviations from normality assumption, a sensitivity analysis for raw number of migraine headache days (total number of migraine headache days for each interval without normalization to 30-day period) will be conducted with a repeated measures negative binomial regression model fitted with SAS PROC GLIMMIX. The model will include treatment, pooled country, month, and treatment-by-month interaction, as well as the continuous fixed covariates of baseline number of monthly migraine headache days and baseline-by-month interaction, log (number of compliant days within each month/30) as the offset in the model. In case of non-convergence, pooled country and/or baseline-by-month interaction may be excluded from the model. Directional consistency of treatment effects from this model and the primary analysis MMRM model as specified in Section 5.5.10.1 will be examined.

In addition, as another form of sensitivity analysis, residuals from the primary analysis MMRM model will be examined and outliers identified. Consistency of results before and after removing patients with outlier residuals will be examined.

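### The log(days/7) offset in the weekly onset model does not correct for missing diary days under a cumulative logit, and the category order that sets its direction is not stated.

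*SAP*

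**What the plan says.** The endpoint, in SAP Table CGAW.4.1 under onset of effect, is "the initial week at which statistical separation in mean change from baseline in the number of weekly migraine headache days is demonstrated" and then maintained for the rest of Month 1. It applies to both the total and the episodic populations.

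SAP 5.5.10.3 treats the weekly count as ordinal with values 0, 1, 2 and so on. For it "a proportional odds model with cumulative logit link will be used", with a random intercept per patient, and then: "Log (number of compliant calendar days within each week/7) will be included as the offset in the model". Weeks with diary compliance at or below 50% are set to missing. The section does not say whether lower or higher counts are accumulated.

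Three other provisions bear on this:

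- The negative binomial sensitivity model in SAP 5.5.10.2 uses the same form of term: "log (number of compliant days within each month/30) as the offset in the model".
- The baseline covariate is already on a 7-day scale: "The weekly baseline number of migraine headache days will be derived as (the monthly number of migraine headache days)/30*7".
- SAP 5.4.1 corrects monthly counts for missing diary days by scaling them by 30 over the number of non-missing days. It also puts all days of Month 1 after day 21 into week 4.

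**The concern.** An offset is a term whose coefficient is fixed at 1. Log exposure works as an offset when the model is for the log of a mean, because halving the observed days halves the expected count. The negative binomial model fits that description under its usual log link, which the SAP does not name. A cumulative logit models the log-odds of falling at or below (or above) each cut-point, and fewer observed days do not shift those log-odds by log(days/7).

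The direction is a separate problem. At a fixed migraine rate, fewer observed days can only lower the count, so P(Y≤j) can only rise. A negative offset added to logit P(Y≤j) pushes it down. Two programmers could follow the SAP faithfully and apply opposite corrections.

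What is at stake is the reported first week of onset, which is decided by week-by-week significance. If galcanezumab patients miss more diary days than placebo patients, that week can come out too early; if placebo patients miss more, too late.

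**Working it through.** **The plan's own figures.** The SAP gives none for this model. Its power figures reproduce and are not affected: with n per arm = 420 × 0.9/2 = 189 and effect size 0.39, power is 96.65% (stated 96%); with 250 × 0.9/2 = 112.5 and 0.46, it is 93.19% (stated 93%).

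**Step 1: one case by hand.** Take a daily migraine probability of 0.3 (assumed), independent days and cut-point P(Y≤1).

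- 7 days: 0.7⁷ + 7(0.3)(0.7⁶) = 0.3294, logit −0.711.
- 6 days: 0.7⁶ + 6(0.3)(0.7⁵) = 0.4202, logit −0.322.
- Shift needed on logit P(Y≤1): +0.39. Offset: log(6/7) = −0.15.

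With lower counts accumulated, the offset contributes −0.15, which is the wrong sign. With higher counts accumulated, it is equivalent to +0.15, the right sign but less than half of what is needed. Lag-1 correlation between days of 0.3 or 0.5 changes the needed shift to +0.27 or +0.20. At the lowest completion kept in weeks 1–3 (4 of 7 days), the needed shifts at correlation 0, 0.3 and 0.5 are +1.34, +0.995 and +0.77, against ∓0.56.

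**Step 2: exact grid.** Days missing at random; 4, 5 or 6 of 7 days observed; daily rate 0.133, 0.2, 0.3 or 0.45; lag-1 correlation 0, 0.3 or 0.5; cut-points 0–3. That is 3 × 4 × 3 × 4 = 144 cells.

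- Lower counts accumulated: wrong sign in 144 of 144.
- Higher counts accumulated: too small in 132. Too large in 12, all at cut-point 0 with clustered days and mostly low rates (needed/supplied 0.68–0.99).
- Median needed/supplied at cut-points 0, 1, 2, 3: 1.26, 1.70, 2.43, 3.47.
- Week 4 of 8–11 full days against 7 (192 cells): wrong sign in all (lower), too small in all (higher).

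**Step 3: effect on the reported onset.** 452 simulated trials per scenario, 210 per arm. Assumed: mean baseline 11.2 migraine days per 30, lag-1 correlation 0.3, days missing at random, months of 28–32 days, separation at Months 2–3. Country was omitted. The SAP's 50% cut-offs were applied. Onset is the first week significant at two-sided 0.05 with all later weeks also significant, counted where Month 1 separated.

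Scenario A has no effect in week 1 and a daily log-odds effect of −0.45 in weeks 2–4. This gives a Month 1 difference of −1.83 days with SD 4.7, a ratio of 0.39. That matches the plan's overall effect size; applying it to Month 1 is an assumption. Scenario B has −0.34 in all four weeks. Entries are the percentage of trials reporting onset in week 1.

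| Missing days, placebo vs galcanezumab | Offset, lower accumulated | No offset | Offset, higher accumulated | Estimated log(days/7) | Binomial | Count × 7/days |
|---|---|---|---|---|---|---|
| A: 9.5% vs 9.5% | 2.5 | 2.5 | 2.5 | 2.5 | 2.9 | 2.9 |
| A: 9% vs 11% | 5.1 | 3.8 | 3.3 | 2.5 | 2.7 | 2.5 |
| A: 7% vs 12% | 13.6 | 8.5 | 4.9 | 1.8 | 2.0 | 2.5 |
| A: 5% vs 15% | 43.8 | 21.9 | 8.3 | 1.6 | 2.0 | 1.8 |
| B: 9.5% vs 9.5% | 43.6 | 45.6 | 46.5 | 47.4 | 47.2 | 46.1 |
| B: 12% vs 7% | 8.3 | 16.1 | 29.3 | 49.2 | 47.0 | 45.2 |

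Monte Carlo standard errors are 0.6–2.4 points. When its coefficient is estimated, log(days/7) averages about 2.2; the plan fixes it at +1 or −1. Count × 7/days was run as week-by-week ANCOVA, standing in for an MMRM.

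**Step 4: a second simulation.** A simpler single-week model under the null, with different assumptions (N = 420, 1,000 replicates, no random intercept), gave two-sided rejection as follows.

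| Missing days, placebo vs galcanezumab | Lower accumulated | No offset | Higher accumulated |
|---|---|---|---|
| 10% vs 10% | 5.1% | 4.9% | 5.1% |
| 5% vs 10% | 22.2% | 13.5% | 8.0% |

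A binomial model and a log-link count model with the same offset stayed between 4.2% and 7.4% in every null scenario, including 5% vs 20% missing. Absolute sizes differ between the two simulations because the assumptions differ. The ordering of the methods agrees.

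**The case against.** The strongest objection concerns materiality. Bias needs diary completion to differ by arm, and the documents give no reason to expect that: Month 1 is double-blind with indistinguishable syringes, entry requires "completion of at least 80% of daily diary entries" in the baseline period, and sparse weeks are dropped. With equal completion the results show no distortion beyond simulation error.

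The plan also has a check in SAP 5.5.7: "Treatment comparisons for ePRO diary compliance for SP III will be performed using an ANOVA". Assuming a per-patient compliance SD of 0.12–0.20, that comparison has 73–99% power for a 5-point gap. It has only 18–40% for a 2-point gap, but there false week-1 onset is 3.3% with higher counts accumulated, close to the 2.5% seen with equal completion.

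The largest figures (13.6% and 43.8%) need both a sizeable gap and the unfavourable category order. With the favourable order, the offset beat no offset in every unequal-completion scenario run. The single-week null rates do not describe an endpoint reached only after a significant primary result and requiring separation to be maintained. An MMRM also treats a small bounded count as normal.

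All of this stands as a limit on the consequence. It does not make the offset valid or supply the missing category order, and the compliance comparison would reveal a gap without correcting it. No option here, including the SAP's own 30/x rule, deals with diary days skipped because of migraine.

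**Conclusion.** The concern holds. The offset is not a valid diary-day correction in this model. Its sign is wrong at every grid point under one reading of the SAP and its size is usually too small under the other. Those results assume only that days are missing at random, over the stated range of rates and clustering.

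The size of the practical harm rests on assumed completion by arm. It is essentially nil with equal completion, small at a 2-point gap, and appreciable from about 5 points, especially if lower counts are accumulated.

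The consequence is confined to one other-secondary endpoint that is conditional (SAP 5.5.10.1 and 5.5.10.3) and unadjusted for multiplicity (Protocol 10.3.3.3). It should be corrected, but it does not threaten the primary or gated conclusions.

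**What to change.** Replace the offset model in SAP 5.5.10.3 with one of these:

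- A binomial events/trials GLIMMIX: migraine headache days out of non-missing diary days in the week, logit link, random patient intercept, the same fixed effects and no offset. Use robust (EMPIRICAL) variance or an overdispersion term, because migraine days cluster.
- An MMRM on weekly count × 7/non-missing days. This matches the 30/x rule, the 7-day baseline and the mean-change endpoint.

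Both also handle a week 4 of 7–11 days (visit interval 30 ± 2 days, minus 21).

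If the ordinal model is kept, at minimum state that higher counts are accumulated, and enter log(days/7) as a covariate with an estimated coefficient. That is an approximate correction.

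The cost is a few SAP sentences, using the same data. The effect scale changes for this one analysis, to a per-day odds ratio (binomial) or a difference in days per week (MMRM).
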